
Statistical Methods
	
 
• In the assessment of efficacy and safety, the following will be calculated for continuous variables: number of subjects, mean, standard deviation, minimum, median, and maximum; categorical variables will be expressed as frequency and percentage.
 
• AEs will be coded using the Medical Dictionary for Regulatory Activities (MedDRA). AEs occurring after administration of the first dose of the study drug will be tallied for the entire study period and for each 3-month sub-period.
 
• Laboratory test values (actually measured values and change from baseline), vital signs (actually measured values and change from baseline), and results of ECG assessment will be tallied at each time point.
 
• Incidence of subject withdrawal due to lack of efficacy will be tallied for the entire study period and each 3-month sub-period. Other efficacy variables will be tallied at each time point.
 

[figure not shown]
- CONFIDENTIAL -

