In the Japanese clinical trial in RA patients (015K-CL-RAJ1), the incidence rates of AEs in the ASP015K 25 mg, 50 mg, 100 mg, and 150 mg groups were 70.9%, 64.9%, 52.7%, and 67.2%, respectively. These rates were comparable with that of the placebo group (64.3%). The incidence rates of AEs whose relationship to the study drug could not be ruled out for the ASP015K 25 mg, 50 mg, 100 mg, and 150 mg groups were 38.2%, 43.9%, 29.1%, and 55.2%, respectively. These rates were higher than that reported for the placebo group (28.6%). By severity (NCI-CTCAE), most were either Grade 1 or Grade 2. In the placebo and ASP015K 25 mg, 50 mg, 100 mg, and 150 mg groups, the numbers of subjects with serious adverse events (SAEs) were 1 (1.8%), 1 (1.8%), 2 (3.5%), 3 (5.5%), and 0, respectively. Death was reported from 1 subject of the 50 mg group (cerebral haemorrhage). AEs resulted in treatment discontinuation in 10 (17.9%), 7 (12.7%), 5 (8.8%), 6 (10.9%), and 4 (6.9%) subjects of the placebo, 25 mg, 50 mg, 100 mg, and 150 mg groups, respectively. The most common reason was rheumatoid arthritis aggravated (21/32). Rheumatoid arthritis, nasopharyngitis, blood creatine phosphokinase (CPK) increased, diarrhoea, cystitis, constipation, stomatitis, dyspepsia, lipids increased, and blood triglycerides increased were reported at  $\geq 5\%$  incidence rates from 1 or more groups. By the MedDRA System Organ Class (SOC), Infections and infestations, Gastrointestinal disorders, Musculoskeletal and connective tissue disorders, and Investigations showed high incidence rates. Blood creatine phosphokinase increased were observed in 0, 2 (3.6%), 1 (1.8%), 1 (1.8%), and 7 (12.1%) subjects of the placebo, 25 mg, 50 mg, 100 mg, and 150 mg groups, respectively. Most cases were transient, and all subjects except 1 who prematurely discontinued the study recovered or

- CONFIDENTIAL -

were recovering. With regard to clinical laboratory testing, compared with the placebo group, the ASP015K groups showed decreased levels of neutrophils, platelets, and estimated glomerular filtration rate (eGFR) and elevated levels of CPK, hemoglobin, lymphocytes, creatinine, total cholesterol, LDL, HDL, and triglycerides. No noteworthy changes were detected in vital signs or ECG recordings.

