### 2.3.2 Efficacy Variables

- The following items at each study visit:
  - ACR20 response rate
  - ACR50 response rate
  - ACR70 response rate
  - Change from baseline in Tender Joint Count (TJC) (68 joints)
  - Change from baseline in Swollen Joint Count (SJC) (66 joints)
  - Change from baseline in DAS28-CRP and DAS28-ESR scores
  - Percentage of subjects achieving DAS28-CRP score for remission
  - Percentage of subjects achieving ACR/EULAR score for remissionACR/EULAR remission is defined as meeting all 4 of the following criteria:
  - TJC  $\leq$  1
  - SJC  $\leq$  1
  - CRP  $\leq$  1 mg/dL
  - Subject’s Global Assessment of Arthritis (SGA)  $\leq$  1 cm (0-100 mm on a VAS scale)
- Percentage of subjects with a SDAI score of  $\leq$  3.3 (SDAI remission)

- CONFIDENTIAL -

- Change from baseline in Physician's Global Assessment of Arthritis (PGA) (VAS)
- Change from baseline in SGA (VAS)
- Change from baseline in the subject's assessment of pain (VAS)
- FACIT-Fatigue score (only in subjects who transferred from study RAJ1)
- Change from baseline in WPAI (only in subjects who transferred from studies RAJ3 or RAJ4)
- Change from baseline in HAQ-DI
- Change from baseline in SF-36v2® score
- Percentage of subjects in EULAR response criterion of "Good Response"
- Percentage of subjects in EULAR response criterion of "Moderate Response"
- Percentage of subjects in EULAR response criterion of "Good Response" or "Moderate Response"
- Incidence of subject withdrawal due to lack of efficacy

[Rationale for efficacy variables]

The efficacy variables were established with reference to "Guidelines on methodology for clinical assessment of antirheumatic drugs" (PFSB/ELD Notification No. 0217001, dated 17 February, 2006), overseas clinical studies of ASP-015K, and other recently reported clinical studies conducted in RA patients.

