### 3.4 Discontinuation Criteria for Individual Subjects

A discontinuation means that a subject who has enrolled in the study prematurely terminates study treatment prior to the completion of all protocol-required elements.

The subject is free to withdraw from the study treatment and/or study for any reason and at any time without giving reason for doing so and without penalty or prejudice. The investigator is also free to terminate a subject's involvement in the study at any time if this is considered necessary because of the subject's clinical condition.

Discontinuation Criteria for Individual Subjects:

The investigator/sub-investigator should discontinue the study if any of the following criteria are met:

1. Subject withdraws consent.
2. The study drug is not sufficiently effective, and a change in treatment method is deemed to be in the subject's best interest by the investigator or sub-investigator.
3. Symptomatic CPK elevation, defined as  $CPK > 1.5 \times ULN$  with severe unusual myalgia, muscular weakness, or muscle twitching\*.  
\* Muscle twitching: A condition in which there is a cramp in a muscle, such as cramps in the calves
4. Any event of myopathy defined as severe unusual myalgia, muscular weakness, and muscle twitching\* regardless of CPK level that persists for at least 2 weeks or that worsens rapidly within 2 weeks.  
\* Muscle twitching: A condition in which there is a cramp in a muscle, such as cramps in the calves
5. Subject infected with HBV who has tested positive for either of or both of HBc and HBs antibodies and is found to be positive for HBV-DNA assay during the study period. Abrupt discontinuance of immunosuppressive therapy may precipitate severe or fulminant hepatitis. Therefore, when HBV reactivates, nucleic acid analog therapy should be immediately initiated, and a hepatologist should be consulted regarding the continuation of ASP015K and concomitant DMARD (unique to Japan: as indicated by "Proposal for Management of Rheumatic Disease Patients with Hepatitis B Virus Infection Receiving Immunosuppressive Therapy" by the Japan College of Rheumatology).

- CONFIDENTIAL -

6. Subject has a malignant tumor.
7. Subject has an adverse event (AE) such as a serious infection, and the investigator or sub-investigator considers that it is not in the subject's best interest to continue the study.

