### **5.2.2 Medical History**

Diseases that remain uncured at the time of the first dose of study drug will be regarded as concurrent diseases. All concurrent diseases will be investigated, and the name of the diagnosis and the time of onset will be recorded in the medical record or other source document, as well as in the CRF (for subjects who were transferred from studies RAJ3 or RAJ4, the onset date of concurrent diseases does not need to be recorded in the CRF). Moreover, AEs that have continued to be present since studies RAJ1, RAJ3, or RAJ4 will be recorded in the CRF.

Previous diseases need not be recorded in the CRF.

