## 5.5 Adverse Events and Other Safety Aspects

### 5.5.1 Definition of Adverse Events (AEs)

An AE is defined as any untoward medical occurrence in a subject administered a study drug that does not necessarily have a causal relationship to this treatment. An AE can therefore be any unfavorable and unintended sign (including an abnormal laboratory finding), symptom, or disease temporally associated with the use of a study drug, whether or not related to the study drug.

All AEs newly observed in the period from the first dose of study drug to end of study (at time of follow-up) or spontaneously reported AEs will be recorded in the medical record or other source document, as well as in the CRF. If a concurrent disease has clearly worsened to an extent that exceeds the usual course after the first dose of the study drug, it will be mentioned among the AEs as a worsening of a concurrent disease. If an AE recurs after having temporarily disappeared, it will be handled as a new AE.

An abnormality identified during a medical test (e.g., laboratory parameter, vital sign, ECG data, physical examination) should be defined as an AE only if the abnormality meets one of the following criteria:

- Induces clinical signs or symptoms
- Requires active intervention
- Requires suspension, interruption, or discontinuation of study medication
- The abnormality or laboratory test value is clinically significant based on the opinion of the investigator or other responsible personnel

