7.2.1 Disposition of Subjects

[Analysis Set: All Subjects with Informed Consent]

The following subject data will be summarized and presented:

- Screened
- Screen failed
- Dosed

[Analysis Set: All Dosed Subjects]

The following subject data will be summarized and presented:

- Subjects who prematurely discontinued from the study period during overall period
- In addition, subjects who prematurely discontinued from the study period will be summarized for primary reason for withdrawal during overall period.
- Subjects who prematurely discontinued from the study period up to 84 months, each interval are as follows:
- In addition, subjects who prematurely discontinued from the study period will be summarized for primary reason for withdrawal up to 84 months
 - \circ 0 1 month
 - 1 <- 3 months
 - \circ 3 <- 6 months
 - 6 <- 12 months
 - 12 <- 24 months
 - o 24 <- 36 months
 - o 36 <- 48 months
 - o 48 <- 60 months
 - \circ 60 <- 72 months
 - o 72 <- 84 months
 - o 84 months <
- Subjects who included/excluded of FAS, SAF, and PDAS

• In addition, subjects who were excluded from FAS, SAF, and PDAS will be summarized by reason for exclusion

[Analysis Set: Subject who experienced dose decrease to 50 mg]

The following subject data will be summarized and presented:

- Subjects who prematurely discontinued from the study period during overall period
- In addition, subjects who prematurely discontinued from the study period will be summarized for primary reason for withdrawal during overall period.

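### The SAP drops the protocol's efficacy variable of withdrawal due to lack of efficacy, and the single-reason disposition count that remains may miss withdrawals for worsening RA

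*SAP*

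**What the plan says.** Protocol 2.3.2 includes among the efficacy variables "Incidence of subject withdrawal due to lack of efficacy". The Statistical Methods part of the Synopsis adds the schedule: "Incidence of subject withdrawal due to lack of efficacy will be tallied for the entire study period and each 3-month sub-period".

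SAP 6.1 (categorical and continuous efficacy endpoints) and SAP Appendix 1 (overview of efficacy analyses) do not contain this variable. The only planned output that could carry it is disposition, SAP 7.2.1: "subjects who prematurely discontinued from the study period will be summarized for primary reason for withdrawal during overall period". The same section repeats that summary in bands of 0–1, 1–3, 3–6, 6–12 and 12–24 months, then yearly to 84 months, then beyond.

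On reasons for stopping, Protocol 3.4 has two criteria that worsening RA could meet. Criterion 2 reads "The study drug is not sufficiently effective, and a change in treatment method is deemed to be in the subject's best interest". Criterion 7 begins "Subject has an adverse event (AE) such as a serious infection, and the investigator or sub-investigator considers" and leaves the decision to the investigator. Protocol 5.2.2 states "Diseases that remain uncured at the time of the first dose of study drug will be regarded as concurrent diseases". Under Protocol 5.5.1, if such a disease clearly worsens beyond its usual course after the first dose, "it will be mentioned among the AEs as a worsening of a concurrent disease".

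Separately, SAP 7.5.1.1 tabulates treatment-emergent AEs (TEAEs) leading to permanent discontinuation, in an overview row and by preferred term.

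**The concern.** A protocol efficacy variable should not disappear between protocol and SAP without a stated reason. Here it survives only as one category in a table of primary reasons, and that category depends on a choice the documents do not define. A flare that ends treatment can satisfy criterion 2. Read literally, RA is also an uncured disease at first dose, so a flare beyond the usual course can be an AE. Protocol 3.4 asks the site for the reason for discontinuation, the SAP counts one primary reason, and neither says which wins when both apply.

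RAJ2 is an open-label extension without a control group, and SAP Appendix 1 plans no hypothesis tests. Retention by reason is therefore one of its main descriptive results. If some sites enter flares as AEs, the lack-of-efficacy figure is too low by an amount nobody can see from the planned tables.

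**Working it through.** **1. Can the 3-month tally be rebuilt from the SAP bands?** Up to 84 months there are 84/3 = 28 three-month sub-periods. Adding the 0–1 and 1–3 month bands gives the first, and the 3–6 month band gives the second. The 6–12 month band merges two sub-periods and each later yearly band merges four. So 2 of 28 can be recovered, and none after month 6.

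**2. Has worsening RA been recorded as an AE leading to discontinuation before?** All inputs are from Protocol 1.3. Its own RAJ1 figure comes first: AE discontinuations for placebo, 25, 50, 100 and 150 mg were 10 + 7 + 5 + 6 + 4 = 32. This matches the denominator in "The most common reason was rheumatoid arthritis aggravated (21/32". The printed percentages imply group sizes of 56, 55, 57, 55 and 58, which sum to the 281 patients in Protocol 1.2.4.

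| Study, period, arms | AE discontinuations | Coded RA | Share | Rate with RA, then without |
|---|---|---|---|---|
| RAJ1, 12 weeks, all five arms | 32 | 21 | 21/32 = 65.6% | 32/281 = 11.4%, 11/281 = 3.9% |
| RAJ3, overall, 100 + 150 mg | 13 + 6 = 19 | at least 3 | at least 3/19 = 15.8% | 19/206 = 9.2%, at most 16/206 = 7.8% |
| RAJ4, overall, 100 + 150 mg | 13 + 12 = 25 | 2 + 1 = 3 | 3/25 = 12.0% | 25/348 = 7.2%, 22/348 = 6.3% |

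The denominators 206 (104 + 102) and 348 (174 + 174) are those implied by the printed percentages. RAJ3 is a minimum because only terms seen in two or more patients are listed, so a single case at 150 mg could be missing. That would make it 4/19 = 21.1%.

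**3. How much of the RAJ1 share is due to arms that RAJ2 does not have?** The protocol does not split the 21 by arm, but bounds follow. If all 10 placebo discontinuations were RA, at least 21 − 10 = 11 of the 22 on active drug were RA (50%). If all 7 at 25 mg were RA too, at least 21 − 17 = 4 of the 15 at 50 to 150 mg were RA (26.7%).

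**4. Absolute scale in the longer studies.** RAJ3 and RAJ4 together give at least 6/44 = 13.6% of AE discontinuations, or about 6 of 206 + 348 = 554 patients (1.1%).

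**5. What cannot be computed.** The documents give no RAJ2 withdrawal counts. They also do not say which primary withdrawal reason the RA-coded patients in the preceding studies were given.

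**The case against.** The case on the other side has four parts.

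First, a reader might infer that the one-reason rule inflates AE discontinuations. It does not. The tables of TEAEs leading to permanent discontinuation are a separate output based on the AE records, so a patient withdrawn for lack of efficacy can also appear there. The preferred-term table will show RA on its own row. What stands is narrower: the overview row can mix efficacy failure with toxicity, and the overlap with the disposition table is not shown.

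Second, a reader might infer that the lack-of-efficacy count is in fact too low. The documents do not support that. The preceding-study figures describe AEs, not primary reasons, and the opposite labelling error is not excluded.

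Third, the protocol is not wholly silent. AE status requires worsening beyond the usual course, so ordinary non-response does not qualify. Protocol 5.2.3 treats RA as the target disease, apart from concurrent diseases, and the rescue-medication rules in 5.1.3.2 name worsening of the primary disease separately from AEs. These limit the overlap. They do not assign a reason when both routes apply, and RA was coded as an AE leading to discontinuation in all three preceding studies.

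Fourth, 66% is a poor guide to RAJ2. It comes from a 12-week trial with placebo and 25 mg arms, while RAJ2 enrols completers who wish to continue and allows dose increases. This stands. The spread between the three studies may also reflect duration and placebo, so it does not show that sites label differently.

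**Conclusion.** The omission is certain: a protocol efficacy variable and its 3-month schedule have no counterpart in the SAP, and the disposition bands cannot replace them after month 6.

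The misclassification is a risk, not a demonstrated bias. The lack-of-efficacy count may be understated because worsening RA has two possible reasons and no rule for choosing. In the preceding studies 12% to 66% of AE discontinuations were RA-coded. For long treatment at 100 and 150 mg, RAJ3 and RAJ4 are the closer guides (at least 15.8% and 12.0%). Carrying any of these figures to RAJ2 assumes similar coding and that the RA-coded cases were not already entered as lack of efficacy. Neither can be checked from the documents.

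The evidence supports a sensitivity count beside the recorded reason. It does not support redefining the endpoint: RA can also flare during a study-drug interruption of up to 4 weeks (Protocol 3.4.1) or when methotrexate (MTX) or another background drug is interrupted or stopped (Protocol 5.1.3.2), and such cases are not clearly failures of the study drug.

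**What to change.** - In SAP 6.1 and Appendix 1, add withdrawal due to lack of efficacy. Tally it as recorded, for the entire period and for each 3-month sub-period.
- Add a sensitivity tally, each subject counted once, of primary reason lack of efficacy or a TEAE leading to permanent discontinuation with preferred term rheumatoid arthritis. Protocol 1.3 uses both rheumatoid arthritis and rheumatoid arthritis aggravated, so confirm that the chosen term in MedDRA 11.1 covers both.
- In SAP 7.5.1.1, add a subject-level row for TEAEs leading to permanent discontinuation that excludes that preferred term.

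The data are already collected: Protocol 3.4 requires the date and reason of discontinuation, and Protocol 5.5.1 requires the action taken with study drug for each AE. The cost is SAP wording and a few extra table rows. The lack-of-efficacy figure may look less favourable, and the sensitivity tally will include some flares caused by interruption of study drug or MTX, which a footnote should say.

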**IV. SYNOPSIS**

Title of Study	Extension Study of ASP015K –Open-Label Extension Study in Rheumatoid Arthritis Patients Who Have Completed Phase IIb Study or Phase III Study of ASP015K– (Protocol Number: 015K-CL-RAJ2)
Planned Study Period	From February 2012 up to a maximum of 6 months after the NDA approval at one of the regions (After the NDA approval in Japan, the post-marketing clinical study will be ended once the study drug is available in the clinical sites as a commercially available product. The planned study period will be up to a maximum of 6 months after the NDA approval in Japan). Sponsor will immediately inform sites when the NDA approval date at one of the regions is confirmed.
Study Objectives	This is an extension study conducted in rheumatoid arthritis (RA) patients who have completed the Phase IIb Study of ASP015K [015K-CL-RAJ1 (hereinafter referred to as study RAJ1)], Phase III Study of ASP015K [015K-CL-RAJ3 (RAJ3)], or Phase III Study of ASP015K [015K-CL-RAJ4 (RAJ4)] to investigate the safety and efficacy of long-term administration of ASP015K.  Another objective of this study is to devise rescue measures for providing the active drug to patients who participated in the Phase IIb Study or Phase III Study of ASP015K, as described in “Guidelines on methodology for clinical assessment of antirheumatic drugs” (PFSB/ELD Notification No. 0217001, dated 17 February, 2006).
Planned Total Number of Study Centers and Location	Approximately 170 centers Japan, Korea, and Taiwan

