3.2 Study Design

This study is an extension study conducted as an open-label, multicenter study in RA patients who have completed studies RAJ1, RAJ3, or RAJ4.

Patients who meet all the inclusion criteria and do not fall under any of the exclusion criteria will receive oral ASP015K 100 mg QD after breakfast as the starting dose. Subjects who have no safety problems but show lack of efficacy may later increase the dose to 150 mg/day. After the increase, the dosage may be reduced from 100 mg/day or 150 mg/day to 50 mg/day at the discretion of the investigator or sub-investigator. The starting dose for subjects who transferred from study RAJ1 is 50 mg/day. For subjects who transferred from study RAJ1 and are continuing to receive 50 mg/day, treatment extension using a dose of 50 mg/day should be allowed when the investigator or sub-investigator considers a dose increase to be inappropriate in terms of safety and treatment extension with a dose of 50 mg/day to provide greater therapeutic benefit for the treatment of RA.

Because this study will end at the point in time when ASP015K is approved, the duration of treatment with the study drug will differ depending on the subject. To prevent purposeless continuation of dosing without effect, the investigator or sub-investigator will assess each subject for efficacy and safety at each visit, confirm the appropriateness of continued administration for each individual, and decide whether or not to continue dosing.

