7 STATISTICAL METHODOLOGY

7.1 General Considerations

- For continuous variables, descriptive statistics will include the number of subjects (n), mean, standard deviation (SD), median, minimum, and maximum.
- For categorical variables: number and percentages of subjects will be described.
- For time-to-event variables: number and percentage of subjects with the event using Kaplan-Meier method, the cumulative event rate will be estimated and a plot will be constructed.
- All data processing, summarization, and analyses will be performed using SAS Drug Development (ver. 4.5), and PC-SAS (ver. 9.4) or higher versions.
- Specifications for table, figures, and data listing formats can be found in the TLF specifications for this study.
- For the definition of subgroups of interest can be referred to Section 7.8.
- Summaries based on FAS and SAF (e.g. disposition, baseline, efficacy data and safety data) will be presented by preceding studies and overall, unless specifically stated otherwise.
- Medical Dictionary for Regulatory Activities (MedDRA) 11.1 will be used as the coding dictionary for adverse event and medical history.
- Confidence interval for binary outcome is continuity corrected in all analysis.
- For the analyses of efficacy and pharmacodynamics variables in this extension study, values at the baseline in the preceding studies (RAJ1, RAJ3, and RAJ4) will be used as the baseline values. However, changes from baseline values of this extension study will also be examined where appropriate. For the analyses of safety, Week 0 of this extension study will be referred to as the baseline; however, changes from baseline values of the preceding studies (RAJ1, RAJ3, and RAJ4) will also be examined where appropriate.
- Change from baseline to post-baseline will be calculated as: post-baseline value baseline value. If the baseline value is missing, then that subject is not included in the calculation at any visit.
- Percent change from baseline to post-baseline will be calculated as: 100 × (change /baseline). If the baseline value is 0 or missing, or post-baseline value is missing, then percent change from baseline to post-baseline is missing.
- The values below the lower limit of quantitation (BQL) for β-D-glucan, hCG, Troponin, CK-MB will be treated as it is and these variables are not used for descriptive statistics

- and displayed in the listings. As for β -D-glucan, it is used for shift-from baseline analysis.

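### Banded discontinuation percentages on all dosed subjects cannot be read as dropout over time, and no planned analysis shows time to discontinuation alone

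*SAP*

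**What the plan says.** SAP 7.2.1 places the banded table under the heading "Analysis Set: All Dosed Subjects". It asks for "Subjects who prematurely discontinued from the study period up to 84 months, each interval are as follows", and for the primary reasons in the same way. The bands are 0–1, 1–3, 3–6 and 6–12 months, then 12-month bands to 84 months, then beyond 84.

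SAP 7.1 sets the statistic: "For categorical variables: number and percentages of subjects will be described". It also sets the columns: "Summaries based on FAS and SAF (e.g. disposition, baseline, efficacy data and safety data) will be presented by preceding studies and overall". SAP 7.2 repeats the population summaries by study region. No section names a number-at-risk base for the bands.

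Follow-up is unequal by design. The protocol synopsis gives the study period as "From February 2012 up to a maximum of 6 months after the NDA approval at one of the regions". SAP 3.2 states: "Because this study will end at the point in time when ASP015K is approved, the duration of treatment with the study drug will differ". Protocol 5.1.1 says that after protocol ver. 2.0/3.0 only RAJ3 and RAJ4 subjects are newly enrolled, and protocol 3.2 requires them to have completed Week 52 of the parent study.

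SAP 7.1 already provides a method for event times: "For time-to-event variables: number and percentage of subjects with the event using Kaplan-Meier method". The Kaplan-Meier plots in SAP 7.3.1 concern dose change. In them, discontinuation either counts as an event together with dose change or is censored. SAP 7.5.1.2 adjusts for unequal duration and differential dropout, but only for adverse events.

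**The concern.** A table of discontinuations by time since first dose invites the reader to follow dropout through the years. Here the late bands contain few events for two reasons unrelated to the risk of leaving: earlier leavers have gone, and later entrants have not been in the study long enough. Both groups stay in the denominator, so falling late percentages can look like fading dropout.

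Retention matters in a long-term extension, since late-visit response rates describe only those who remain. The by-reason bands carry extra weight. Withdrawal for lack of efficacy is a listed efficacy variable in protocol 2.3.2, and the protocol synopsis promises it overall and by 3-month sub-period. SAP 6.1 and Appendix 1 do not list it, so the bands in 7.2.1 are its only time-resolved analysis in the SAP.

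The region columns are exposed too. Protocol 1.2.4 places RAJ1 in Japan, and protocol 1.3 says RAJ4 included only Japanese subjects. Korea and Taiwan therefore contribute RAJ3 subjects only. In bands that RAJ3 subjects cannot reach, those columns are zero whatever their true retention.

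**Working it through.** **Stated inputs (SAP 4).** About 800 treated; 201 from RAJ1; planned sources of 300 (RAJ3) and 510 (RAJ4). 201 + 300 + 510 = 1,011. A total of 800 implies 800 − 201 = 599 from RAJ3/RAJ4, or 599/810 = 74% roll-over. The plan states no roll-over or dropout rate, so 800 cannot be reproduced and serves only as a denominator.

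**Assumed inputs.**
- Constant annual dropout d = 10% (range 5–20%).
- Stop in November 2019, the SAP page date: 93 months after February 2012.
- Uniform RAJ1 entry over months 0–12.
- Uniform RAJ3/RAJ4 entry over months 41–65 (July 2015 to July 2017).

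For the earliest RAJ3/RAJ4 entry, one reference behind the dose rationale is dated September 2013. Adding 52 weeks of parent study gives about September 2014, or month 31. Maximum follow-up is then 93 − 31 = 62 months.

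**Dilution before attrition.** Where only RAJ1 can contribute, the pooled base is too large by 800/201 = 4.0.

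**Months 60–72, d = 10%.** At risk: 201 × 0.9^5 = 118.7. Events: 118.7 × 0.10 = 11.9.
- Share of all dosed: 11.9/800 = 1.5%.
- Share of the RAJ1 column: 11.9/201 = 5.9%.
- Share of those at risk: 11.9/118.7 = 10.0%.

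**Later yearly bands, d = 10%, pooled column** (events and numbers at risk are expectations under the assumed entry and stop):

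| Months | At risk | Events | % of 800 | % of at risk |
|---|---|---|---|---|
| 12–24 | 720.0 | 72.0 | 9.0 | 10.0 |
| 24–36 | 648.0 | 59.6 | 7.5 | 9.2 |
| 36–48 | 437.6 | 33.0 | 4.1 | 7.6 |
| 48–60 | 197.5 | 14.3 | 1.8 | 7.3 |
| 60–72 | 118.7 | 11.9 | 1.5 | 10.0 |
| 72–84 | 106.8 | 10.4 | 1.3 | 9.7 |

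If everyone were followed past 84 months, the 72–84 share of all dosed would be 0.9^6 × 0.10 = 5.3%. Staggered entry and the stop reduce it to 1.3%. In the RAJ1 column that band is 5.2% of all dosed against 9.7% of those at risk, and most of that gap is earlier attrition.

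**Sensitivity.**
- d = 5%: months 60–72 give 1.0% against 5.0%; months 72–84 give 0.9% against 4.9%.
- d = 20%: months 60–72 give 1.7% against 20.0%; months 72–84 give 1.3% against 19.4%.
- Earliest RAJ3/RAJ4 entry (months 31–55), d = 10%: months 60–72 give 1.5% against 8.2%; months 72–84 are unchanged.
- Stop at month 71 (January 2018, the date of SAP version 1.00), d = 10%: months 36–48 already give 1.8% against 10.0%, and bands from 72 months are empty.

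**Early bands, d = 10%.** With everyone followed for at least a year, shares of all dosed are:
- 0–1: 1 − 0.9^(1/12) = 0.9%
- 1–3: 0.9^(1/12) − 0.9^(1/4) = 1.7%
- 3–6: 0.9^(1/4) − 0.9^(1/2) = 2.5%
- 6–12: 0.9^(1/2) − 0.9 = 4.9%
- 12–24: 0.9 − 0.9^2 = 9.0%

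The percentages rise first, purely because the bands widen.

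**Number at band start as the only base.** For the first five bands this gives 0.9, 1.7, 2.6, 5.1 and 10.0%, an apparent acceleration. It then gives 7.6% and 7.3% at 36–60 months, because some subjects reach the study stop inside the band. The patient-year rate is −ln(0.9) = 10.5 per 100 in every band.

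**The case against.** SAP 7.2.1 contains no sentence fixing the percentage base, and SAP 7.1 leaves table formats to separate specifications that are not part of these documents. This stands: the all-dosed base is the plain reading of the set heading plus the percentage rule, not an explicit statement.

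A share of all dosed subjects is a normal disposition partition, and the bands add up to total discontinuation. This also stands. A reader might infer that the late-band figures are wrong. The documents do not support that; the figures are correct for what they measure.

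A reader might also infer that the percentages would fall steadily from the first band at constant risk. They would not: with the SAP's unequal bands they rise to 12–24 months and fall only afterwards.

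The preceding-study columns remove most of the entry mismatch, and the exposure table in SAP 7.3.1 uses the same cut-points, so numbers at risk could be approximated by hand. That softens the problem. It does not help the overall and region columns, and no retention estimate is planned from it.

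Finally, the table is descriptive. No test, sample size or efficacy estimate changes.

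**Conclusion.** The point holds as a matter of interpretation and of a missing analysis. Under staggered entry and an approval-driven stop, all-dosed band percentages cannot be read as dropout over time, and nothing else planned shows time to discontinuation alone.

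Dilution is strongest in the overall and region columns. It is about 4-fold in the pooled column once only RAJ1 subjects can contribute, and about 5- to 15-fold at 60–84 months after attrition at 5–20% per year. In the RAJ1 column at 10% it is a little under 2-fold.

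These sizes rest on assumed entry windows, stop date, constant dropout and a 201/599 split. The documents give none of these except the 201 and the total of about 800. The direction does not depend on the particular values, given unequal follow-up. The change is worth making because it decides whether the study can describe long-term retention.

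**What to change.** Keep the all-dosed counts and percentages as the partition of total discontinuation, and state the denominator in SAP 7.2.1.

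Add a Kaplan-Meier estimate and curve of time from first RAJ2 dose to premature discontinuation. Censor subjects who complete at study end, and show numbers at risk at the band cut-points, by preceding study and overall. Read the overall tail with care, since it may consist of RAJ1 subjects only.

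For primary reasons, above all lack of efficacy and adverse event, give cumulative incidence with the other reasons as competing events. Alternatively, give events per 100 patient-years by band, as SAP 7.5.1.2 does for adverse events.

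Do not rely on the count divided by the number at band start alone, because it ignores censoring within bands and still varies with band width.

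The cost is a short SAP addition and one or two more outputs. The data are already collected and SAP 7.1 already names the Kaplan-Meier method.
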